7.4 Statistical Analyses

7.4.1 Primary Safety Analyses

Summaries and analyses of safety data will be presented for the Safety Analysis Population.

Solicited AEs will be summarized overall and by maximum severity post through study day 7, post study period days 7 -14 and overall. Additionally, solicited AEs will be analyzed by taking the most severe response (grouped as either modified per protocol or per protocol), dichotomizing into a binary variable (none versus mild, moderate, or severe) and using standard techniques, such as exact confidence intervals (CI), to summarize the proportion of subjects reporting each solicited sign or symptom.

Unsolicited non-serious AEs will be collected from the time of first device use through study day 14. Unsolicited AEs will be coded by MedDRA™ for preferred term and system organ class (SOC). All SAEs will be collected from the time of first device use through the study day 14. The number of SAEs will be reported by detailed listings showing the event description, MedDRA™ preferred term and SOC, study day of occurrence, severity, relatedness, and outcome for each event. Non-serious unsolicited AEs will be summarized as number and percentage of subjects reporting at least one event in each MedDRA□ preferred term and SOC, cross tabulated by severity and relationship to the study device. Additionally, the proportion of subjects and exact 95% CIs of AEs in aggregate and by MedDRA□ categories will be computed.

Clinical laboratory data, including methemoglobin measurements, will be summarized by severity and as the maximum numeric value over the entire study. Graphical presentations may include box plots and shift plots.

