5.5.3 Investigator Decision to Discontinue Subject Use of Device

A subject may be removed from the study for the following reasons post initial device use; however, whenever possible the subject should be followed for safety evaluations per protocol:

- Study non-compliance to protocol requirements that in the opinion of the participating clinical site PI or appropriate sub-investigator poses an increased risk (e.g., missing safety labs) or compromises the validity of the data.

- Lost to follow-up. (*A subject will be considered lost to follow-up if he or she fails to appear for a follow-up assessment. Extensive effort (i.e., generally three documented contact attempts via telephone calls, e-mail, etc., made on separate occasions) will be made to locate or recall the subject, or at least to determine the subject's health status. These efforts will be documented in the subject's study file.*)
- Medical disease or condition, or new clinical finding(s) for which continued participation, in the opinion of the participating clinical site PI or appropriate sub-investigator, might compromise the safety of the subject, interfere with the subject's successful completion of this study, or interfere with the evaluation of safety.
- If any AE, clinical laboratory abnormality or situation occurs such that continued participation in the study would not be in the best interest of the subject.
- The occurrence of a SAE.
- If the subject is using the device in any manner inconsistent with instructions and protocol directives and procedures.

If the subject agrees, every attempt will be made to follow all AEs through resolution or stabilization.

Subjects who withdraw, or are withdrawn from this study, or are lost to follow-up after signing the informed consent form (ICF) and use of the RD19 device will not be replaced. Subjects who withdraw, or are withdrawn from this study, or are lost to follow-up after signing the ICF but before use of the device may be replaced.

The reason for subject discontinuation or withdrawal from the study will be recorded on the appropriate e-CRF.

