5.5.4 Follow-up of Study Subjects Who Discontinue Device Use

Discontinuation of study device use does not constitute discontinuation from the study, and the study procedures for early termination should be completed as indicated by the SOA (Table 3). If a clinically significant finding is identified, including, but not limited to, changes from baseline, after enrollment, the participating clinical trial site PI or qualified designee will determine if any change in subject management is needed. Any new clinically relevant finding will be reported as an AE.

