7.3 Populations for Analyses

The full safety analyses population is by intention-to-treat (ITT) including all subjects who received at least a single use of RD19.

A modified per protocol population for analyses will include all study volunteers who complied with study procedures and remained on study, per protocol, until at least the day 7 clinic visit.

The per protocol population for analyses will include all study volunteers who complied with all protocol procedures and remained on the study until their day 14 visit.

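### The per-symptom solicited-AE proportions and exact CIs are stated only for the two per-protocol sets, so subjects who react and leave early can drop out of them

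*Combined protocol and SAP*

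**What the plan says.** Section 7.4.1 begins with a general rule: "Summaries and analyses of safety data will be presented for the Safety Analysis Population". Section 7.3 defines the safety population as everyone who used RD19 at least once.

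Three statements in Section 7.4.1 then bear on solicited AEs:

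- **Maximum-severity summary.** "Solicited AEs will be summarized overall and by maximum severity post through study day 7", then for Days 7 to 14, and overall. No other set is named, so the general rule applies.
- **Additional per-symptom analysis.** Here "solicited AEs will be analyzed by taking the most severe response (grouped as either modified per protocol or per protocol"). Each symptom is reduced to none versus any severity, and the proportion of subjects reporting it is summarised with methods such as exact confidence intervals. No confidence level is given.
- **Later CI sentence.** In the paragraph on unsolicited AEs, the plan adds "the proportion of subjects and exact 95% CIs of AEs in aggregate" and by MedDRA category.

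Section 7.3 defines the modified per-protocol set as "all study volunteers who complied with study procedures and remained on study, per protocol, until at least the day 7 clinic visit", and the per-protocol set as "all study volunteers who complied with all protocol procedures and remained on the study until their day 14 visit".

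Section 5.5.3 lists reasons for which a subject may be removed after first use. They include an SAE, use inconsistent with the instructions, and this one: "If any AE, clinical laboratory abnormality or situation occurs such that continued participation in the study would not be in the best interest". Subjects removed after using the device are not replaced. Section 5.5.4 adds: "Discontinuation of study device use does not constitute discontinuation from the study".

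**The concern.** Safety and reactogenicity is the primary objective, and Section 7.1 describes the study as one that obtains preliminary estimates of them. The proportion of subjects with each solicited symptom, with its interval, is such an estimate. The one sentence that clearly plans it names two sets whose membership can depend on the outcome being estimated.

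A subject who has a reaction and is then removed, withdraws, or is judged non-compliant stays in the safety population but can fall outside one or both per-protocol sets. If reactors are excluded more often than others, the tabulated proportion is too low. In a study of 25, one such exclusion can turn an observed reaction into a zero in that table. Section 7.2 draws its conclusions from exactly the case in which no AE of a given type is seen.

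**Working it through.** **Step 1. Which set applies to which analysis.**

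| Section 7.4.1 analysis | Set | Interval planned? |
|---|---|---|
| Solicited AEs by maximum severity and period | Safety (opening rule; no other set named) | None mentioned |
| Each solicited symptom, none versus any | Modified per protocol or per protocol, as written | Exact CI, level not stated |
| AEs in aggregate and by MedDRA category | Safety (opening rule) | Exact 95% CI, but placed with the unsolicited AEs |

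Only the second row clearly gives a proportion with an exact CI for each solicited symptom, and the safety population is not among the sets it names.

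**Step 2. Who can be lost.** From Sections 7.3, 5.5.3 and 5.5.4:

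- Leaves the study before the Day 7 visit: in the safety set, in neither per-protocol set.
- Complies, and leaves between the Day 7 and Day 14 visits: in the safety and modified per-protocol sets, not in the per-protocol set.
- Stops the device but stays on study: Section 7.3 does not say whether this subject still counts as having complied.

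**Step 3. Size.** The plan has no figure of its own to reproduce here, and the documents give no symptom or exclusion counts. The counts below are assumptions. N = 25 comes from Section 4. The 95% level is borrowed from the later CI sentence.

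Formula (Clopper-Pearson, x affected out of n): lower limit = 2.5% quantile of Beta(x, n − x + 1); upper limit = 97.5% quantile of Beta(x + 1, n − x). For x = 0 the lower limit is 0 and the upper limit is 1 − 0.025^(1/n).

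Five of 25 subjects have a given symptom:

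| Excluded from the per-protocol set | x/n | Proportion | Exact 95% CI |
|---|---|---|---|
| Nobody | 5/25 | 20.0% | 6.8 to 40.7 |
| 1 affected | 4/24 | 16.7% | 4.7 to 37.4 |
| 2 affected | 3/23 | 13.0% | 2.8 to 33.6 |
| 3 affected | 2/22 | 9.1% | 1.1 to 29.2 |
| 3 unaffected | 5/22 | 22.7% | 7.8 to 45.4 |

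One of 25 subjects has the symptom:

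- Safety set: 1/25 = 4.0% (0.1 to 20.4).
- That subject excluded: 0/24 = 0%, upper limit 1 − 0.025^(1/24) = 14.2%.

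The first four rows show the downward shift, the last row shows that the direction can reverse, and the single-reactor case shows an observed reaction tabulated as none in this analysis.

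**The case against.** The strongest reply is that the opening rule covers both summaries and analyses, so it reaches this sentence too. On that reading the parenthesis adds a grouping to the safety-set presentation and does not restrict it. Section 7.4.2, by contrast, assigns acceptability to the per-protocol sets in plain terms. This reading is possible, but the safety set is still not named where the sets are listed, and a programmer following the sentence as written would produce only per-protocol results. The wording needs correction under either reading.

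Second, the later CI sentence refers to AEs without the word unsolicited, and Section 6.2.1 counts solicited events as AEs. It may therefore be meant more broadly than its paragraph. Even so, it gives intervals in aggregate and by MedDRA category, which does not clearly mean one for each solicited symptom.

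Third, the maximum-severity summary keeps early reactors, and a safety-set proportion could be derived from it by collapsing the grades. That stands: no event disappears from all reporting, and what is not clearly planned is a safety-set interval for each symptom.

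Fourth, exclusions may be few. Section 5.5.3 asks for continued safety follow-up whenever possible, and Section 7.2 assumes that subjects will likely complete. That also stands, and with no exclusions the sets coincide. Completion alone is not enough, however: the per-protocol set also requires compliance with all procedures, and daily diary cards are among them.

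Finally, the study tests no hypothesis, and the pausing rules do not use these sets. This limits the consequence to the reported estimates, which are the purpose of the study.

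**Conclusion.** The concern holds. Section 7.4.1 contradicts its own population rule for the per-symptom solicited-AE proportions and exact CIs, and as written it permits exclusions that depend on the outcome. It should be fixed.

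The size depends on counts that the documents do not give. In the illustration the proportion falls from 20.0% to between 16.7% and 9.1% when one to three of five affected subjects are excluded, and from 4.0% to 0% when a lone reactor is. The bias is zero if all subjects comply and complete, and it is upward if those excluded are mainly unaffected. The subject-set ratios planned in Section 7.4.3 would show how many were excluded, but not their symptom rates. The text does not prove that a safety-set version would never be produced, only that it is not clearly planned.

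**What to change.** In Section 7.4.1, replace the parenthesis in the additional solicited-AE sentence with: in the Safety Analysis Population (all subjects with at least one use of RD19). Keep the modified per-protocol and per-protocol versions as supportive tables.

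The cost is one phrase and no new data. Reported rates may look less favourable than the per-protocol ones if subjects with reactions were excluded from those sets.

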| Physical Examination | X | *Targeted only | *Targeted only | *Targeted only |
| BMI | X | | | |
| Vital Signs | X | X | X | X |
| Methemoglobin | X | *Before and 60 minutes after device use | *Before and 60 minutes after device use | *Before and 60 minutes after device use |
| Lab Sample Collection & Processing | X | | | X |
| CBC and differential | X | | | X |
| CMP | X | | | X |
| Urinalysis | X | | | X |
| Urine Pregnancy Test | X | | | X |
| Concomitant Medication History/New | X | X | X | X |
| Device Illumination | | X | X | X |
| Acceptability Assessment of Device | | X | X | X |
| Distribution and train diary card | | X | | |

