3. STUDY DESIGN

3.1 Overall Design

This first-in-man (FIM) phase I study will evaluate the acute safety, tolerability, and device acceptability for use among 25 healthy volunteers between the age of 18 and 45. Based on the results of numerous preclinical studies, a single dose (9 joules/cm²) and schedule (twice a day, separated by at least 4 hours, preferably 8 to 12 hours apart) will be evaluated.

Safety and tolerability (local reactogenicity) will be assessed actively at the following study days: screening (baseline set), 1, 7 and 14, and on non-clinic visit days by collection of these data by history during clinic visits via a memory aid (diary cards). Volunteers will be encouraged to promptly contact designated clinical trial staff or the one of the Sponsor's Emergency Response Team for AEs of a medically urgent nature.

A Comprehensive Metabolic Panel, as well as CBC with differential, urinalysis, and pregnancy testing will be performed at screening and at Day 14 or early termination (and potentially during unscheduled) clinic visits. Hematological safety assessments (evaluation of methemoglobinemia) will be performed at all visits.

Study volunteers will be asked to immediately contact the clinical coordinator and/or the PI in all instances where they experience an AE of greater than moderate intensity. Volunteers will be instructed to report to the clinical trial unit for an unscheduled visit or to seek the appropriate level of medical care based on the nature of their AE/SAE. In all such instances, all relevant information pertaining to these significant medical events will be captured on the appropriate e-CRFs.

Hematology safety laboratory evaluations will be performed at screening, as well during all scheduled clinic visits. Laboratory assessments may be part of the evaluation of medically attended AE evaluation and for all SAEs.

Upon ratification of the CTA, the site will begin pre-recruitment outreach efforts of potential volunteers within M3-WRA's database to ascertain "interest in general" in this study. Official recruitment which may include fliers, letters, telephone calls, etc. and specific recruitment of potential subjects who have previously participated in other clinical studies conducted at the site will occur only after formal IRB approval. Other forms and/or mechanisms of recruitment may also be used. The IRB will approve the recruitment process and all materials prior to use.

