 - Reactogenicity assessments will include an assessment of illumination site reactions – erythema, edema/induration, pain and difficulty swallowing, as well as systemic reactions—fever, chills, headache, and nausea. Pre-illumination reactogenicity assessments will be performed immediately prior to first RD19 use to establish a baseline, then the use of the RD19 device will occur.
- Subjects will be observed in the clinic for at least 60 minutes post each RD19 illumination. The illumination site will be examined, post-use reactogenicity assessments will be performed, and any AEs/SAEs will be recorded on the appropriate e-CRF prior to discharge from the clinic. The oropharynx and surrounding tissues will also be examined on Days 1, 7, 14 and during unscheduled visits and early termination visits.
- Vital signs:
- Vital sign measurements will include systolic and diastolic BP, HR, and oral temperature. Vital signs will be measured at timepoints specified in the SOA. On Days 1, 7 and 14, vital sign measurements will be collected prior to device administration. Vital signs assessed on Day 1 prior to the first use of RD19 will be considered as baseline. Subjects must not eat or drink anything hot or cold within 10 minutes prior to taking their oral temperature or using the RD19 device.
- Clinical laboratory evaluations:
 - Fasting is not required before collection of clinical laboratory evaluations.
 - Urine pregnancy test will be performed locally by the site laboratory at the screening visit and at the final study visit. Results must be confirmed as negative prior to randomization on Day 1 and allocation and use of the RD19 device.
 - Clinical screening laboratory evaluations (CMP and CBC (diff) will be performed locally by the site laboratory).
 - Clinical safety laboratory evaluations will be performed locally by the site laboratory.
 - Methemoglobin will be measured prior to use of the device in the clinic and just prior to discharge from the clinic after 1 hour.
 - Blood and urine will be collected at timepoints specified in the SOA.

○ Diary Cards:

- All subjects will complete a Diary Card daily for the entire term of the study. Diary Cards will be reviewed with the subjects for any AEs (solicited injection site and systemic reactions, as well as unsolicited AEs), SAEs and concomitant medications. Diary Cards will be collected at the end of a volunteer's participation in the study.

○ Acceptability Assessment:

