7.4.3 Baseline Descriptive Statistics

Summaries of demographic variables such as age, sex, ethnicity, and race will be presented. Summaries of baseline clinical laboratory values will be presented.

Absolute numbers and ratios of Screened:Enrolled, Enrolled:Modified Per-Protocol and Enrolled:Per-Protocol will be presented.

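### Laboratory values are summarised numerically only as a whole-study maximum, which can be a reading from before any device use and leaves the before/after methemoglobin pairs unused

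*Combined protocol and SAP*

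**What the plan says.** Section 7.4.1 commits to two summaries of on-study laboratory data: "Clinical laboratory data, including methemoglobin measurements, will be summarized by severity and as the maximum numeric value over the entire study". The sentence after it is permissive: "Graphical presentations may include box plots and shift plots". Section 7.4.3 adds, for baseline alone, "Summaries of baseline clinical laboratory values will be presented". No section commits to a minimum, a by-visit value, a change from baseline or a before/after difference.

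The data for such summaries are collected. In the Schedule of Activities (Section 1.2, Table 3), methemoglobin is read at screening and then, on Days 1, 7 and 14, "Before and 60 minutes after device use". Section 6.2 agrees: "Methemoglobin will be measured prior to use of the device in the clinic and just prior to discharge from the clinic after 1 hour". Table 3 places CBC, CMP and urinalysis at screening and at Day 14 or early termination.

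Two definitions bear on the maximum. Section 1.1.4 measures the duration of the whole study from the start of screening to the last subject's last visit. Section 6.2 fixes a baseline for vital signs, "Vital signs assessed on Day 1 prior to the first use of RD19 will be considered as baseline", and likewise places the reactogenicity baseline just before first use. It gives no such rule for methemoglobin, which is read both at screening and before use on Day 1.

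**The concern.** A reading taken shortly before device use is informative mainly by comparison with the reading an hour later. The plan collects three such pairs per subject, and Section 3.1 singles the measurement out: "Hematological safety assessments (evaluation of methemoglobinemia) will be performed at all visits". Yet the one committed numeric summary pools all readings and keeps the highest. Some of those readings precede any exposure to the device, and for a quantity that might fall, such as a blood count, the highest value is the wrong end of the range.

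There is no control arm (Section 7.2), so the subject's own earlier value is the only comparator for laboratory data. At stake is how well this first-in-man study can describe movement in laboratory values, mainly the acute movement in methemoglobin. The endpoints in Section 3.2 (adverse events, serious adverse events and acceptability) are not at stake.

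**Working it through.** The plan states no figure on this point, so there is nothing to reproduce. The figures below are illustrations. The documents give no laboratory SDs, so the unit is the within-subject SD of one reading. Except in step 1, readings are assumed independent and normal.

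**Inputs.** Table 3 gives 1 screening reading plus 2 × 3 visit readings = 7 methemoglobin readings per completer. Two precede any device use (screening, Day 1 pre-use) and 5 follow first use, of which 3 are the 60-minute readings. n = 25 (Section 3.1).

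**1. Where the maximum falls when the device does nothing.** If the 7 readings are exchangeable, and ties aside, each is equally likely to be the highest. P(maximum precedes any exposure) = 2/7 = 28.6%. P(maximum is not a 60-minute reading) = 4/7 = 57%. Neither figure needs normality.

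**2. What the maximum registers when there is an effect.** E[max] is obtained by numerical integration.

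| Scenario | Max of all 7 | Max of the 5 after first use | Maximum precedes exposure (7 readings) |
|---|---|---|---|
| No effect | 1.35 | 1.16 | 28.6% |
| +1 SD at each 60-minute reading, no carry-over | 1.97 (moves 0.62) | 1.92 (moves 0.75) | 10.6% |
| +1 SD at all 5 later readings | 2.19 (moves 0.84) | 2.16 (moves 1.00) | 6.6% |

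The two effect patterns give nearly the same maximum: 1.97 against 2.19, or 1.92 against 2.16.

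**3. What change from the Day 1 pre-use reading registers.** Take the five later readings in order: Day 1 post, Day 7 pre, Day 7 post, Day 14 pre, Day 14 post. The expected changes are:
- no effect: 0, 0, 0, 0, 0
- acute rise: 1, 0, 1, 0, 1
- sustained rise: 1, 1, 1, 1, 1

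This series separates the patterns by itself. The post-minus-pre change at each visit (acute 1, 1, 1; sustained 1, 0, 0) restates it in the form the paired design suggests.

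**4. Precision of a mean change.** The 95% half-width is t(0.975, 24)/√25 = 2.064/5 = 0.413 SD of the differences. With independent readings the SD of a difference is √2, giving 0.413 × 1.414 = 0.58 within-subject SD.

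**5. CBC and CMP.** Under Table 3 there are two scheduled values. If screening counts, the maximum is the larger of the two. For normal readings with means 0 and −δ, E[max] = −δ·Φ(−δ/√2) + √2·φ(δ/√2).
- No change (δ = 0): √2 × 0.3989 = 0.56.
- A true 2 SD fall (δ = 2): −2 × 0.0786 + 1.414 × 0.1468 = 0.05.

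So after a 2 SD fall the mean maximum still lies slightly above the screening mean of 0. If screening is excluded and data are complete, the maximum is simply the Day 14 value. Its mean minus the baseline mean then equals the mean change, and only the paired interval is missing.

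**The case against.** The strongest reply is that the summary suits its purpose. Looking for methemoglobinemia means asking whether anyone reaches an abnormal level, and severity plus the highest value answers that. Section 6.1.2 makes abnormal post-use laboratory findings adverse events, Section 6.2.8 grades them, and Section 5.5.4 has clinically significant findings, changes from baseline among them, assessed individually and new clinically relevant ones reported. The study tests no hypothesis (Section 7.1). All of this stands and limits the point to descriptive reporting.

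Four stronger readings are tempting but not supported:
- **That laboratory harm would go unseen.** The sections just cited say otherwise. Nor can it be said that falls go ungraded: the severity summary rests on the Appendix 2 tables, which are not in the text available for this review.
- **That the plan compares a maximum with a single baseline value and so builds in a spurious rise.** No section plans that comparison; the baseline summaries stand apart in Section 7.4.3. The no-effect excess of 1.35 SD is a caution against making it later.
- **That the window of the maximum is wholly undefined.** Section 1.1.4 starts the study at screening, so the better reading is that pre-exposure values are included.
- **That within-subject change would isolate a device effect.** Without controls it also contains time and visit effects. Inclusion criterion 10 requires screening values within normal ranges and out-of-range values may be repeated, so some later drift out of range is expected with no effect. This matters most for CBC and CMP, whose baseline is the screening value.

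It is also fair that the sizes have no clinical scale. Methemoglobin is read by pulse oximetry (Section 6.1.1) and the documents give no resolution or repeatability. Same-visit correlation of 0.5 to 0.95 would lower the no-effect excess over seven readings from 1.35 to between 1.28 and 1.12, a modest change.

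Finally, step 5 of the working relies on Table 3. Section 3.1 limits CBC to screening and Day 14, yet elsewhere has hematology evaluations at every scheduled visit, and Section 6.1.1 lists CBC under hematology. These statements must be reconciled; the two-reading figures hold only for Table 3's schedule.

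**Conclusion.** The point holds as a modest gap in a supporting safety summary. On its natural reading the planned maximum includes pre-exposure readings, which would supply it in about 29% of subjects if the device has no effect (seven exchangeable readings). It cannot show falls in CBC or CMP values, barely distinguishes an acute from a sustained methemoglobin rise, and leaves the three before/after pairs without a committed analysis. The loss is the descriptive estimate of within-subject change, mainly the acute methemoglobin change. The primary endpoint is unaffected.

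The reading of the text is firm. The SD-unit sizes are illustrative and rest on independent normal readings, complete data and the Table 3 schedule.

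**What to change.** In Section 7.4.1:
- Keep the severity summary. Define the maximum as the highest value after first device use, which excludes screening and Day 1 pre-use readings.
- State the baseline: Day 1 pre-use for methemoglobin, screening for CBC and CMP.
- For methemoglobin, add the mean change with a 95% interval from Day 1 pre-use to each later reading, and show the post-minus-pre change at Days 1, 7 and 14 beside it.
- For CBC and CMP, add the change from baseline to Day 14 or early termination, and the post-baseline minimum alongside the maximum.
- Label the intervals descriptive, and note that uncontrolled change includes time effects and regression after selection on normal screening values.
- Reconcile the hematology timing in Section 3.1 with the Schedule of Activities.

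A full shift table is not needed: with screening values required to be normal, it would be close to a single row.

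The cost is some SAP wording and a few extra tables. No new visits, samples or data are required.
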